5.1 Design

This is a four-arm, randomized, controlled trial to test the effectiveness of gamification, financial incentives, or both to increase physical activity among individuals with a 10-year ASCVD risk score of 7.5% or higher. There will be a 2-week run-in period to obtain baseline measures of physical activity, followed by a 12-month intervention period and then a 6-month follow-up period.

Participants will use the Penn Way to Health research technology platform to provide informed consent and complete eligibility surveys. Eligible patients will be mailed a wearable activity tracker that captures data on daily steps counts and minutes of MVPA. They will be asked to use the device for two weeks to get accustomed to it. During this period, we will use a protocol from prior work to estimate a baseline step count using the second week of data. The first week of data will be ignored to diminish the tendency for use of devices in week 1 of receiving a new device to be significantly higher than what might be observed at steady state. To prevent risk of mismeasurement, we will ignore any daily values less than 1000 steps because evidence indicates these values are unlikely to represent capture of actual activity.^{15,16} At least four days of data must be available during that second week to estimate baseline measures; otherwise the period will be extended. In prior work, we typically have 6 to 7 days of data from more than 90% of participants.¹² Participants who do not complete this run-in phase will not be randomized into the trial. Participants will also complete a series of validated surveys including risk preferences (DOSPERT),¹⁷ social support (Medical Outcomes Study),¹⁸ personality (Big Five) and health-related quality of life (EQ-5D).¹⁹⁻²¹ See table in Section 8.2 for full list of surveys and timing

--Goal Setting--

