Once baseline measures have been established, participants will be contacted to choose their goals using an approach we have found to work well in previous studies. They will be given their baseline step count and asked to select a step goal increase of 33%, 40%, 50% or choose a custom goal as long as it is at least 1500 steps greater than baseline. We have used this approach in the past because it gives participants the options of setting their own goal but also steers people to choose one of the options provided, any of which would be terrific from the standpoint of increasing physical activity. Leaving it completely open-ended risks having participants either pick goals that are ‘too easy’ or not likely to be attainable. In prior work, we find that on average participants chose ambitious goals and more than half selected a 50% step increase.

--Randomization—

Participants that have established baseline measures and finished goal selection will be randomly assigned to control or one of the three interventions using a 1:2:2:2 allocation and stratifying on baseline step count (< 4000 steps, 4000 – 7000 steps, > 7000 steps) using an electronic number generator through the Way to Health research technology platform. We do this because it preferentially increases power for comparison between the different intervention arms, as the differences between intervention arms are likely to be smaller than the difference between the intervention arms and control.

--Study Arms—

All participants will be asked to use the wearable device during the day and at night to measure activity. Each participant will primarily receive study communications by text message. Interventions by study arm will vary as follows:

--Arm 1: Control—

During the intervention and follow-up periods, participants in this arm will receive a daily text message stating whether or not they achieved their step goal on the prior day.

--Arm 2: Gamification intervention—

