8.2 Procedures

After providing informed consent, participants will complete an online questionnaire to confirm eligibility and complete the study surveys. Eligible participants will be mailed a wearable activity tracking device to wear for about two weeks to collect a baseline step count.

Participants will select step goals and then be randomly assigned as described in the Study Design section.

Surveys and interviews will be conducted as outlined in the Table:

Area	Name	# Questions	Baseline	6 Months	12 Months	18 Months	Validation Study
Screening Survey	NA		X				
Baseline (demographics)	NA		X				
Cardiovascular history/Weight/Meds	NA		X	X	X	X	
Health status	EQ-5D-5L and EQ-VAS	6	X	X	X	X	Janssen MF, Pickard AS, Golicki D, Gudex C, Niewada M, Scalone L, Swinburn P, Busschbach J. Measurement properties of the EQ-5D-5L compared to the EQ-5D-3L across eight patient groups: a multi-country study. Qual Life Res. 2013;22(7): 1717-1727.
Exercise self-efficacy	Self-Efficacy for Exercise Behaviors	12	X	X	X	X	Sallis JF, Pinski RB, Grossman RM, Patterson TL, Nader, PR. The development of self-efficacy scales for health-related diet and exercise behaviors. Health Education Research. 1998;3:283-292.
Sleep	Pittsburg Sleep Quality Assessment	9	X	X	X	X	Buysse DJ, Reynolds CF, Monk TH, Berman SR, Kupfer DJ. The Pittsburgh Sleep Quality Index: A new instrument for psychiatric practice and research. Psychiatry Research. 1989;28:193-213
Mood	PHQ9	9	X	X	X	X	Kroenke K, Spitzer RL, Williams JB. The PHQ-9: validity of a brief depression severity measure. J Gen Intern Med. 2001;16(9):606-613.
Social Support	MOS Social Support	19	X	X	X	X	Sherbourne CD, Stewart AL. The MOS social support survey. Soc Sci Med. 1991;32(6):705-714.
Risk Preferences	DOSPERT	30	X				Blais A, Weber EU. A domain-specific risk-taking (DOSPERT) scale for adult populations. Judgement and Decision Making. 2006;1(1):33-47.
Personality	Big Five	44	X				John OP, Srivastava S. The Big-Five trait taxonomy: History, measurement, and theoretical perspectives. In L. A. Pervin & O. P. John (Eds.), Handbook of personality: Theory and research. New York: Guilford Press. 1999;2: 102-138.
Grit	Grit Scale	10	X				Duckworth AL, Quinn PD. Development and validation of the short grit scale (grit-s). J Pers Assess. 2009;91(2):166-174.
Qualitative survey	NA				X	X	
Interviews						X	

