9.1 Power and sample size

Physical activity has been demonstrated to have a direct dose relationship with reduction in the risk of cardiovascular disease and events, with even small increases significantly lowering risk.^{6,22-25} We use 1000 steps as our threshold for powering statistical significance, which for the average person is about half a mile and takes about 10 minutes of MVPA.²⁶ Based on our prior work,¹⁰⁻¹⁴ we estimate a standard deviation in the primary outcome of 2500 steps. This study has been powered for six comparisons

between arms using a common cutoff for the test statistics that ensures the familywise error rate is at most 0.05. This is the approach suggested in Follmann et al.²⁷ and it generalized Tukey's Honest Significant Differences approach for an unbalanced design. We estimate that a sample of 1050 participants allocated in a 1:2:2:2 distribution (150 in control and 300 in each intervention arm), will ensure 93% power to detect a 1000 step difference between each intervention arm and control, with a standard deviation of 2500 steps and an 8-minute difference in MVPA assuming a standard deviation of 20 minutes. This calculation assumes a 10% dropout rate. We estimate that we will have at least 85% power to detect a 750-step difference with a standard deviation of 2500 steps and a 6-minute difference in MVPA with a standard deviation of 20 minutes.

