9.2 Comparative-effectiveness analysis

Prior to analyses, we will produce data summaries to assess data quality, examine data distribution, and randomization success. All analyses will be performed using intention-to-treat. Data can be missing for any day if the participant did not use the activity tracking device or did not upload data. For the main analysis we will use multiple imputation for step values that are missing or less than 1000 steps. We will perform five sets of imputations and results will be combined using Rubin's standard rules.²⁸ We will perform sensitivity analyses to assess the robustness of the findings using only collected data with and without step values less than 1000 steps. Since minutes of MVPA are derived from step counts, this process should address missing data for MVPA as well.

Similar to prior work,¹² the primary analysis will fit linear mixed effect regression models to evaluate changes in physical activity outcomes measures (primary and secondary outcomes) adjusting for each participant's baseline measure, time using calendar month fixed effects, participant random effects, and accounting for repeated measures. Secondary analyses will fit linear mixed effect regression models adjusted for other variables of interest such as participant demographic characteristics and cardiovascular history. Exploratory analyses will fit logistic mixed effect regression models to evaluate the proportion of weeks that CDC guidelines for physical activity were achieved.

We will perform subgroup analyses using available participant sociodemographic characteristics including age, sex, race/ethnicity, education, and income level. We will also conduct subgroup analyses using differences in baseline measures such as baseline step count and atherosclerotic cardiovascular disease (ASCVD) 10-year risk score. If differences in outcomes exist, we will fit a fully adjusted model that includes these covariates and interaction terms with the treatment arms to evaluate for statistical significance.

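### Section 9.2: adding a short, closed list of baseline covariates to the primary model would be a cheap efficiency improvement; the planned model is valid, and the size of the gain is unknown

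*Combined protocol and SAP*

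**What the plan says.** Section 9.2 specifies a linear mixed model for the primary and secondary outcomes, "adjusting for each participant's baseline measure, time using calendar month fixed effects, participant random effects, and accounting for repeated measures". Read naturally, the baseline measure is the baseline value of whichever outcome is modelled: steps for step outcomes, MVPA for MVPA outcomes. No other participant-level baseline variable enters the primary model.

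The remaining predictors come later in the same section: "Secondary analyses will fit linear mixed effect regression models adjusted for other variables of interest such as participant demographic characteristics and cardiovascular history". That wording gives examples. It does not close the list, and no functional forms or missing-covariate rule follow.

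The survey table in section 8.2 shows that demographics and "Cardiovascular history/Weight/Meds" are collected at baseline. Section 8.2 places the questionnaires before the run-in and randomisation. Existing ASCVD is part of the inclusion criteria in section 5.5.

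The baseline step count comes from the second run-in week only, and section 5.1 sets this minimum: "At least four days of data must be available during that second week to estimate baseline measures". Randomisation is done "stratifying on baseline step count", so for steps the primary model already covers the stratification variable.

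**The concern.** The baseline covariate is a mean over one week, possibly over only four days, and it has to predict a mean over about 44 weeks (12 months less the 8-week ramp-up, section 3.1). Such a baseline can leave between-person variation that age, sex or existing ASCVD might partly explain. Accrual runs over two years (section 5.4), so baseline weeks fall in different seasons. The month terms are given as "time using calendar month fixed effects". They describe when the outcome was observed, and the month in which baseline was measured is not listed.

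Any variance these covariates explain would reduce the standard error of all six pairwise comparisons, because one model serves all arms. Under the present plan such a gain would appear only in a secondary analysis whose covariates are not fixed, and which therefore carries little confirmatory weight.

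**Working it through.** **Inputs from section 9.1.** SD 2500 steps; 150 control and 300 per intervention arm; 10% dropout; 1000 steps against control at 93% power; 750 steps at no less than 85% power. On multiplicity: "This study has been powered for six comparisons". One shared critical value holds the overall type I error at 0.05.

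**Assumptions.** Tests are two-sided. The 750-step figure refers to one intervention against another; against control, 750 steps has only 66.8% power even without dropout. Participants who drop out contribute nothing. The SD of 2500 is the residual SD after baseline adjustment. The extra variance explained beyond the baseline measure, R², is not in the documents and is varied from 0 to 0.10.

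**Common cutoff.** Simulating the largest of the six pairwise |Z| statistics under 1:2:2:2 allocation (2 million draws) gives c = 2.566, a nominal two-sided level of 0.0103 per comparison.

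**Formulas.** SE = 2500 × √(1 − R²) × √(1/n₁ + 1/n₂). Power = Φ(difference/SE − c).

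**The plan's own figures, no dropout (150/300), R² = 0**
- Against control: SE = 2500 × √(1/150 + 1/300) = 250. Power = Φ(1000/250 − 2.566) = Φ(1.434) = 92.4%, close to the stated 93%.
- Between interventions: SE = 2500 × √(2/300) = 204.1. Power = Φ(750/204.1 − 2.566) = 86.6%, consistent with the stated 85% or more.

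**With the stated 10% dropout (135/270), R² = 0**
- Against control: SE = 2500 × √(1/135 + 1/270) = 264, power 89.0%.
- Between interventions: SE = 2500 × √(2/270) = 215, power 82.1%.

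The stated power therefore reproduces only when dropout is not applied. That is a separate matter, but it sets the starting point here.

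**Effect of extra covariates, 135/270**

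| Extra R² | SE vs control | SE between interventions | Fall in SE | Power, 1000 vs control | Power, 750 between interventions |
|---|---|---|---|---|---|
| 0 | 264 | 215 | 0% | 89.0% | 82.1% |
| 0.01 | 262 | 214 | 0.5% | 89.4% | 82.6% |
| 0.05 | 257 | 210 | 2.5% | 90.8% | 84.4% |
| 0.10 | 250 | 204 | 5.1% | 92.4% | 86.6% |

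An R² of 0.10 returns exactly the no-dropout figures, because the variance factor 0.9 cancels the 10% loss of participants.

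**If 2500 is not the residual SD.** Section 9.1 calls it the SD of the primary outcome, which section 3.1 defines as a change. Suppose, for illustration, that the planned baseline adjustment already removes 10% of that variance. With 135/270, power against control then starts at 92.4%. A further 5% gives SE = 250 × √0.95 = 243.7 and power Φ(1000/243.7 − 2.566) = 93.8%. The gain is 1.4 points, against 1.7 points in the table (89.0% to 90.8%, from unrounded values).

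**The case against.** The strongest reply is that nothing is wrong with the planned model. It is prespecified, its covariate set is closed, and it already contains the baseline value of the outcome, which is usually the strongest predictor. Adding covariates is a design preference. This stands, and it is why the point is only an improvement.

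It also stands that the gain is assumed. The documents give no variance explained by age, sex, ASCVD status or baseline month, so a range starting at zero is the only fair one. The 2500 may not be a residual SD, in which case the gain shrinks as shown.

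The cost is not nil. Month as a categorical term adds 11 parameters. Completeness of the survey items is not documented, and section 9.2 itself speaks of the sociodemographic characteristics that are available.

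A reader might infer that the open list lets the primary result be chosen after the data are seen. The documents do not support that: the illustrative wording governs only the secondary models and cannot change the six primary comparisons. What remains is that those secondary models cannot firmly corroborate the primary result until their covariates are named.

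**Conclusion.** The point holds as a low-cost efficiency improvement. The primary model has one participant-level prognostic covariate, further predictors are collected before randomisation, and a short fixed list in a linear model with 1050 participants is easy to support. Under the assumptions listed, the gain is between 0 and 3.4 points of power against control (92.4 − 89.0) and between 0 and 4.5 points between interventions (86.6 − 82.1). The upper ends need an extra R² of 10%, for which the documents give no evidence.

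Three stronger readings should be resisted. The model does not adjust for baseline steps alone: calendar month is in it, and the MVPA models would use baseline MVPA. The documents do not show that the primary standard errors are materially too wide, or that precision is being given away free, because the extra R² may be near zero and the covariates bring parameters and missing values. Nor is there bias: the covariates at issue are fixed before randomisation, so leaving them out affects precision only.

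**What to change.** In section 9.2, define the primary model as the outcome's baseline measure, the calendar-month terms, and a closed list: age as a continuous term, sex, existing ASCVD (yes/no), and season or month of the baseline week. Use baseline values only, and state how a missing covariate is handled. Fix the list before anyone sees outcomes by arm, and keep the present model as a named sensitivity analysis. If the primary model is left as it is, at least replace the illustrative wording for the secondary models with a named list, functional forms and the same missing-value rule.

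The cost is a few sentences in the SAP and no new data. The model gains up to 14 parameters with month categorical (1 for age, 1 for sex, 1 for ASCVD, 11 for month), or 6 with four seasons (1 + 1 + 1 + 3).

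### Arm-by-covariate interactions are tested only if undefined differences are seen in the same data, so the subgroup tests that are run and reported are a selected set

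*Combined protocol and SAP*

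**What the plan says.** Section 9.2 lists five sociodemographic factors: "We will perform subgroup analyses using available participant sociodemographic characteristics including age, sex, race/ethnicity, education, and income level". It adds "baseline measures such as baseline step count and atherosclerotic cardiovascular disease (ASCVD) 10-year risk score". That makes seven named factors, and the wording leaves both lists open.

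The next sentence sets the rule for formal testing: "If differences in outcomes exist, we will fit a fully adjusted model that includes these covariates and interaction terms with the treatment arms". The stated purpose of that model is to use "interaction terms with the treatment arms to evaluate for statistical significance".

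The section does not say what counts as a difference, how large it must be, for which outcome or arm contrast, or whether it is judged by eye or by a test. Nowhere else do the documents plan an unconditional interaction test, a rule to report every subgroup result, or a multiplicity rule for subgroups. The common cutoff in section 9.1, which "ensures the familywise error rate is at most 0.05", covers the six between-arm comparisons only.

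**The concern.** The arm-by-covariate interaction is the valid test of whether an effect differs between subgroups. Here it is run only after a difference has been seen, and that difference is closely related to the statistic the interaction model then tests. This is a stated decision rule, not only a missing detail. Followed literally, it decides which tests exist by looking at their likely result.

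Two things are at stake. Readers would see interaction p-values that look like ordinary 5% tests but were chosen because a difference had appeared. And a factor that does not meet the trigger gets no interaction test, even if its true interaction is sizeable, for example when both levels respond clearly but by different amounts.

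**Working it through.** The documents give no figure for subgroup or interaction tests, so there is none to reproduce. The check asks what the conditional rule does under explicit meanings of the trigger.

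**Inputs from section 9.1.** SD: "we estimate a standard deviation in the primary outcome of 2500 steps". Group sizes: "150 in control and 300 in each intervention arm". Dropout: "This calculation assumes a 10% dropout rate", which leaves 270 and 135.

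**Assumptions, not in the documents.** One binary factor split 50/50; one intervention-versus-control contrast; normal estimates; two-sided tests at 0.05; and two possible triggers: (a) significant in one level but not in the other, (b) an observed difference of at least 500 steps between the two level-specific effects.

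**Standard errors without dropout.**
- Effect within one level (150 vs 75): 2500 × √(1/75 + 1/150) = 353.6.
- Interaction: 353.6 × √2 = 500, so p<0.05 needs an observed difference of 1.96 × 500 = 980 steps.
- After dropout these become 372.7, 527 and 1033.

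**No true interaction, trigger (b).** The trigger is met with probability 2 × [1 − Φ(500/500)] = 0.317. Every significant interaction (over 980 steps) also meets it, so the share of tests run that are significant is 0.05/0.317 = 15.8%. After dropout it is 0.05/0.343 = 14.6%. A stricter 750-step trigger gives 0.05/0.134 = 37% (32% after dropout).

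**No true interaction, trigger (a).** With power p in each level, the trigger is met with probability 2p(1 − p). The joint probability with a significant interaction comes from simulation.

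| Uniform true effect | p | Trigger met | Met and p<0.05 | Significant among tests run | Same, after dropout |
|---|---|---|---|---|---|
| 750 steps | 0.564 | 49% | 4.9% | about 10% | about 10% |
| 1000 steps | 0.807 | 31% | 4.3% | about 14% | about 12.5% |

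At a true effect of zero the trigger is met in about 9.5% of cases, 3.1% are met and significant, and the conditional share is about 33%.

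**Unconditional error.** The probability that a null factor both meets the trigger and shows p<0.05 is the fourth column, or 5.0% under trigger (b). It never exceeds 5%, because the condition can only remove rejections.

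**True interaction present: share of otherwise significant interactions never tested (no dropout).**

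| True effects in the two levels | Trigger (a) | Trigger (b) |
|---|---|---|
| 2000 vs 800 | 47% (40% after dropout) | 0% |
| 1500 vs 500 | 9% | 0% |
| 1000 vs 0 | 7% | 0% |
| 1500 vs 0 | 4% | 0% |

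Trigger (b) blocks none because 980 exceeds 500. Trigger (a) blocks most when both levels are likely to be significant on their own.

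**Alternative reading: differences between arms overall.** Then the trigger does not depend on the interaction estimate, and the conditional rate is 5.0%. Interactions can still go untested. With 270 vs 135, the SE of the overall contrast is 2500 × √(1/135 + 1/270) = 263.5. The common cutoff for six comparisons at the planned allocation is about 2.57 by simulation. The chance of no overall significance is then about Φ(2.57 − 1000/263.5) = 11% at a true effect of 1000 steps, 75% at 500 and 99% at zero.

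**The case against.** The strongest reply is that the plan defines no trigger, so every figure above rests on a definition supplied here. That stands: the figures show a range of behaviour and do not predict what the trial will do. It does not rescue the sentence, because any trigger based on observed subgroup differences selects the tests that are run.

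A reader might infer that the rule inflates the false-positive rate. The calculations do not support that: the unconditional error per factor stays at or below 5%. The distortion lies in the tests that are run and reported.

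A reader might also infer that real interactions will certainly be missed, or that about half will be. That does not follow either. The 47% needs one particular trigger and one particular pair of true effects. Under the same trigger the other three scenarios give 4% to 9%, and under the 500-step trigger the loss is nil.

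Nor should the problem be sized by the chance of at least one false positive over seven factors, 1 − 0.95^7 = 30% if the tests are independent. That is multiplicity under unconditional testing; it would also apply to a corrected plan that tests all seven without adjustment.

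The between-arm reading is open. It removes the selection of p-values but leaves interactions untested whenever no overall difference is seen.

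Finally, one could say that subgroup work is only exploratory. Section 9.2 does not label it so. It uses that word for the models of meeting the CDC activity guideline, and it gives the interaction model the task of assessing statistical significance.

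**Conclusion.** The concern holds in a limited form. Section 9.2 makes its only test of subgroup differences depend on an undefined look at the same data. On the natural reading, about 10% to 16% of the interaction tests actually run would show p<0.05 with no true interaction, against a nominal 5%, and more with a stricter step threshold. This rests on the 50/50 split, a single contrast, a uniform effect of 750 to 1000 steps and the two assumed triggers.

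The harm is selective testing and reporting. The share of otherwise significant interactions left untested ranges from 0% to about 47% in the cases checked. If the sentence refers to differences between arms, only the untested interactions remain as a problem. The primary comparison and the familywise control of the six arm comparisons are not touched.

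**What to change.** Replace the conditional sentence in section 9.2 with text along these lines:

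> For each named subgroup factor (age, sex, race/ethnicity, education, income, baseline step count, ASCVD risk score) we will fit the arm-by-factor interaction in the mixed model regardless of observed subgroup results. For every factor we will report a global interaction test with subgroup estimates and confidence intervals. These analyses are exploratory.

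If the team wants to claim significance for any factor, the last sentence should instead state Holm adjustment across the factors. Naming the factors also closes the two open lists; categories or cut-points should be fixed at the same time. Whether factors enter one at a time or together in a fully adjusted model is a matter of preference, provided that the choice is stated and no factor depends on what the data show.

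The cost is a few extra model fits on data already collected and a longer results table. No participants, visits or measurements are added.
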